### **Research plan and methodology**

The proposed study will have two aims: i) to determine the feasibility of an empowerment-based CBT-I in MCI persons; and ii) to examine the preliminary effects of the empowerment-based CBT-I on sleep, cognitive outcomes and HRQoL in persons with MCI. Sleep pattern in terms of time to initiate sleep (sleep latency, SL), number and duration of awakenings after sleep onset (WASO), ratio of total sleep time (TST) to the time spent in bed (sleep efficiency, SE) and sleep quality will be the primary outcomes, and cognitive function and HRQoL will be the secondary outcomes.

### Study design

This will be a mixed-method study with a single-blinded parallel-group randomized controlled trial (RCT) and a qualitative study to determine the feasibility and preliminary effects of the empowerment-based CBT-I on sleep, cognitive outcomes and HRQoL in persons with MCI. The study implementation protocol is outlined in Figure 1. A research assistant (RA1) will recruit eligible participants from the elderly community centers operated by two non-governmental organizations in Hong Kong. After collecting the baseline data (T0), RA1 will randomly assign participants into the intervention group and control group with block randomization to ensure even distribution of participants in the two study groups over the study period. A computer-generated random sequence will be used to determine the block size (6, 8 and 10) and respective study group allocation in a 1:1 ratio. To ensure allocation concealment, the group allocation will be determined according to the random sequence codes placed in sealed opaque envelopes. Participants in the intervention group will receive the empowerment-based CBT-I, whereas the control group will receive usual care. To minimize biases, another research assistant (RA2) who is blinded to the group allocation will be responsible for collecting post-test data immediately (T1) and 3 months (T2) post-intervention for both groups. A total of 10 participants, with 3-4 participants from each intervention group, will be invited to take part in a qualitative interview to obtain more in-depth comments about the feasibility and acceptability of the intervention.

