A five-step empowerment approach (Figure 2) will be adopted to implement each face-to-face session to facilitate goal attainment and behavioral maintenance. At the beginning of each session, RA1 will encourage the participants to discuss their usual practice or beliefs about sleep or insomnia related to the core area of that week. The RA1 will make use of various therapeutic communication and counseling skills during the process, which are outlined in Figure 2. Moreover, supportive, non-judgmental and empathetic attitudes will be used to build a rapport with the participants. The RA1 will then deliver a structured educational session about the topic area. The rationales and explicit methods of how to carry out the suggested behaviors will be stated. The content will emphasize assisting participants to understand the linkage between their usual practice (behaviors/thoughts) and the consequences to sleep disruption. The RA1 will then facilitate the participants to identify the discrepancies between their usual practice/dysfunctional beliefs and the recommended best practice for sleep improvement/beliefs that favor better sleep. Easy-to-understand comic stories will be incorporated to illustrate the more abstract concepts about dysfunctional beliefs related to insomnia (for the session on cognitive therapy) and bed-sleep association (for the session on stimulus control). The RA1 will also highlight the possible consequences of these discrepancies on brain health. The RA1 will then assist participants to set self-directed goals related to these areas. During this process, the RA1 will work collaboratively with the participants and ensure that the goals are achievable yet challenging. The RA1 will also work with the participants to develop an action plan for achieving the goals set during each session. After action-planning, a subsequent interactive skill-building session will ensure that participants acquire the skills required to perform specific behaviors. A scenario-based approach will be adopted to train the participants on how to maintain the recommended behaviors. The RA1 will make use of group dynamics by encouraging the discussion among the peers of successful actions, feelings, concerns and perceived barriers to goal achievement. Various memory compensatory strategies will be used to reinforce the educational content, such as memory aids (e.g., memory notebooks, calendars and to-do lists) and mnemonic strategies. Each subsequent session will begin with a discussion of progress in goal attainment and challenges and barriers encountered while implementing the action plan set during the preceding week. The RA1 will also review the key messages delivered in previous sessions.

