
The RA1 will provide continuous support through telephone calls (two bi-weekly calls) upon the completion of all face-to-face sessions. A telephone record containing the participants' demographic and clinical profile, endorsed dysfunctional beliefs and attitudes about sleep, self-directed goals and action plans will be created to facilitate the telephone support. The RA1 will monitor participants' adherence to the recommended behaviors and goal attainment progress, identify barriers in real-life settings and provide methods of resolving them. The advice and counseling given will be documented to guide subsequent telephone calls.

Control group: Usual care

The control group will receive the standard care provided by the elder community centers. The participants in the control group are required to consent not to participate in any structured cognitive training activities provided by the centers during the study period.

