#### Fidelity monitoring of the study intervention

A step-by-step standard manual with sample dialogue will be developed to guide the RA1 in delivering the intervention. Moreover, the PI will randomly select two groups in the intervention arm for fidelity monitoring and checking. The face-to-face sessions will be videotaped, and the telephone calls will be audiotaped after obtaining the participants' consent. A performance checklist will be developed and used for fidelity checking. Two postdoctoral fellows will be invited to review the videos and complete the checklist. In addition, the attendance of the participants will be recorded. All of these data will be used to interpret the study findings.

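### One unblinded research assistant recruits, takes baseline, assigns and treats, so the next arm can be guessed better than chance (about 66% against 50%) despite varied blocks and opaque envelopes

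*Combined protocol and SAP*

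**What the plan says.** Study design gives three pre-treatment tasks to one person. On recruitment: "A research assistant (RA1) will recruit eligible participants from the elderly community centers operated by two non-governmental organizations in Hong Kong". On allocation, once RA1 has taken the T0 measures: "RA1 will randomly assign participants into the intervention group and control group with block randomization".

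The section on the intervention group gives the same person the treatment: "The RA1 will then deliver a structured educational session about the topic area". After the face-to-face sessions, "The RA1 will provide continuous support through telephone calls".

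Study design also states two safeguards. A computer-generated sequence is "used to determine the block size (6, 8 and 10) and respective study group allocation in a 1:1 ratio", and the codes are placed in sealed opaque envelopes. A second assistant, RA2, is blinded, but only the T1 and T2 data collection is given to RA2.

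The protocol does not say who generates the sequence, who prepares, holds or opens the envelopes, whether they are sequentially numbered, whether RA1 is kept unaware of the block sizes, or whether participants are randomised singly or in cohorts.

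**The concern.** Envelopes hide the next code but not the codes already opened. RA1 treats the intervention arm, so RA1 knows who is in it and, having recruited everyone, who is not. Every completed block is balanced, so the running difference between the arms equals the difference within the current block. Guessing the arm that is behind therefore works without knowing the block size.

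A recruiter who can guess the next arm can, even without intending to, influence who enters it through whom to approach and when. Taking baseline before assignment does not control who comes next. One entry criterion, functional independence, rests on an interview rather than a score; the protocol does not name the interviewer. RA1 also takes the T0 measures while able to guess the arm.

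At stake is the effect estimate. Under Study participants, the pilot is meant to supply the effect size for planning a full-scale trial, so selection bias here would carry into that trial's sample size.

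**Working it through.** The documents give no predictability figure, so there is none to reproduce.

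**Inputs from the protocol.** Block sizes 6, 8 and 10 and 1:1 allocation (Study design); 60 participants, 30 per arm (Study participants); RA1's roles as quoted above.

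**Assumptions not in the protocol.** One unstratified sequence; the three block sizes equally likely; participants randomised one at a time; RA1 remembers all earlier allocations.

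**1. Fixed blocks, closed form.** For block size 2m, the expected share of correct guesses under the arm-behind rule (a coin toss when level) is [m + (2^(2m)/C(2m,m) − 1)/2] / 2m.
- Size 6: [3 + (64/20 − 1)/2]/6 = 4.10/6 = 68.3%
- Size 8: [4 + (256/70 − 1)/2]/8 = 5.329/8 = 66.6%
- Size 10: [5 + (1024/252 − 1)/2]/10 = 6.532/10 = 65.3%

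**2. The protocol's varied blocks, by simulation of sequences of 60.**

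| Blocks | Certain assignments | Correct guesses |
|---|---|---|
| 6, 8, 10 at random | 1.7% (about 1 of 60) | 66% |
| 6 fixed and known | 25% | 68% |
| 8 fixed and known | 19% | 66% |
| 10 fixed and known | 17% | 65% |

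With varied blocks, about 71% of simulated trials contain no certain assignment. The best possible guess, using the set of block sizes, and the simple arm-behind rule both give 66%. Varying the block size removes nearly all certainty but hardly lowers the average guess rate.

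**3. Where the 66% comes from.** The arms are level before about 33% of assignments, where the guess is 50%. Before the other 67% the guess is right about 74% of the time: 0.33 × 0.50 + 0.67 × 0.74 = 0.66.

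**4. What it could do to the estimate (illustration).** Suppose RA1 enrols people d SD better in prognosis when expecting intervention, d SD worse when expecting control, and does not steer when the arms are level. The expected difference between arms is 2d × (2 × 0.66 − 1) = 0.64d.
- d = 0.10: 0.06 SD
- d = 0.25: 0.16 SD

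For scale, the standard error of a difference in means at 30 per arm is √(2/30) = 0.26 SD.

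**The case against.** **The safeguards are real.** A reader might infer that the next assignment is simply predictable. The documents do not support that: with varied blocks and opaque envelopes only about 1 assignment in 60 is certain, against 25% with known fixed blocks of 6. What remains is a guess better than chance.

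**The 66% is not an envelope failure.** It already assumes that future codes are perfectly hidden. It arises from balanced blocks combined with a recruiter who knows past allocations. The 50% comparator is therefore a recruiter unaware of past allocations, not one using better envelopes. It also follows that an independent envelope holder alone leaves the 66% unchanged, because RA1 still learns allocations as therapist.

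**A guess rate is not a bias.** This stands. The 0.06 to 0.16 SD depends on an assumed d and is below one standard error. But sampling error is reported with the estimate, whereas selection bias is not visible in it.

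**Analysis could help.** A reader might infer that the bias could not be removed at all. That is too strong. Cognition and sleep are measured at screening or T0, so imbalance in them can be seen and adjusted for. Only unmeasured traits, such as motivation, escape this.

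**Motive and opportunity are partly inferred.** Nothing in the protocol says that RA1 has a stake in the result, and the point does not need it. Most entry criteria are scored cut-offs or listed exclusions, which limits discretion over eligibility but not over whom to approach and when.

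**Randomisation may be by cohort.** Therapy runs in groups of 6 to 8, so participants may be allocated in batches, which would reduce the risk. The protocol does not say so.

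**Conclusion.** The concern holds in a limited form. RA1 recruits, takes baseline, assigns and treats, and can guess the next arm correctly about 66% of the time against 50% for a recruiter unaware of past allocations. Selection through timing or choice of whom to approach is therefore possible, and baseline covariates could correct it only in part. That RA1 knows the earlier allocations is inferred from the stated roles, but the inference is sound.

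The 66% depends on the assumptions listed above; cohort randomisation would lower it. The bias of 0.06 to 0.16 SD is an illustration, not an estimate: nothing in the documents shows that steering would occur. Separately, control of the envelopes is unspecified, so the concealment that the protocol claims cannot be verified from its text. The change should be made before recruitment, because it is cheap and the unmeasured part of any bias cannot be undone later.

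**What to change.** Amend Study design in two parts.

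**Secure the sequence and the baseline.** A team member without participant contact, for example the principal investigator, generates the sequence, keeps sequentially numbered envelopes and the block sizes from RA1, and releases each code only after consent, eligibility and T0 are logged. RA2 takes the T0 measures; they precede allocation, so RA2's blinding is unaffected. This prevents early or out-of-order opening and takes baseline measurement away from someone who can guess the arm. It does not lower the 66%.

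**Lower the guess rate, by one of two routes.**
- Enrol a whole cohort and complete its baseline before any allocation in it is revealed. With 1:1 allocation, an intervention group of 6 to 8 implies a cohort of 12 to 16, which can be built from whole blocks (6 + 6, 6 + 8, 8 + 8 or 6 + 10). With whole blocks no imbalance carries into the next cohort, and the guess rate is 50%.
- Or have someone unaware of past allocations confirm eligibility and fix the enrolment order. RA2, who is meant to stay blinded, could do this.

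State in either case whether randomisation is single or by cohort.

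**Cost.** A short protocol edit, one message per participant or cohort, some baseline time moved from RA1 to RA2, and a short wait between baseline and allocation. No new staff are needed.

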### **Outcome measures**

Sleep assessment. Three measures were chosen to evaluate sleep pattern and quality by both subjective and objective means according to the recommendations suggested by the international expert consensus.[52] The 19-item Chinese version of the PSQI will be used to assess subjective sleep quality.[53] It is reliable (Cronbach's alpha = 0.83) and has shown good test-retest reliability and discriminant validity.[53] The Chinese version of the Insomnia Severity Index (ISI-C) (7-item)[54] will be used to assess the perceived insomnia severity, consequences of insomnia and the degree of distress related to insomnia. A five-point Likert scale is used, with higher values indicating higher levels of perceived severity of insomnia, more severe consequences of insomnia and a greater degree of distress associated with insomnia. The ISI-C has good internal consistency (Cronbach's alpha = 0.81), construct and discriminant validity.[54] An Actiwatch, which contains an accelerometer to record the frequency and intensity of body movement, will be used to objectively assess sleep patterns. The parameters of sleep pattern include TST, SL, WASO and the ratio of TST to SE. Participants will be instructed to wear the Actiwatch on their non-dominant wrist during sleep for a consecutive seven-day period.

Cognitive assessments. To detect subtle cognitive changes, a battery of cognitive assessments will be used to evaluate various domains of cognition, including the Cantonese version of the Alzheimer's Disease Assessment Scale—Cognitive subscale (ADAS-Cog)[55] for global cognition, the digit span-forward and backward test for attention and working memory, the Hong Kong List Learning Test for episodic memory, and the Color Trails Test for complex attention, executive function and task switching.

HRQoL. The Chinese Hong Kong version of the Short Form Health Survey (SF-12) will be used to measure HRQoL.[56] It consists of 12 items to form two summary scores to reflect people's physical and mental well-being, with higher scores indicating better HRQoL. Its psychometric properties are satisfactory with evidence of good reliability, content and construct validity.[56]

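### Baseline cognitive tests are given by RA1 and follow-up tests by RA2, so change from baseline on these secondary outcomes crosses assessors; RA2 could give both

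*Combined protocol and SAP*

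**What the plan says.** All references are to the combined protocol and SAP.

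- **Baseline.** Study design: "After collecting the baseline data (T0), RA1 will randomly assign participants into the intervention group and control group". The natural reading is that RA1 does the T0 assessment and that it is complete before allocation.
- **Follow-up.** The same section says that "another research assistant (RA2) who is blinded to the group allocation will be responsible for collecting post-test data", at T1 and T2 and in both arms. The stated purpose is to reduce bias.
- **Therapist.** The description of the intervention group gives delivery to RA1: "The RA1 will then deliver a structured educational session about the topic area".
- **Outcome ranking.** Research plan and methodology lists the sleep-pattern measures and ends: "sleep quality will be the primary outcomes, and cognitive function and HRQoL will be the secondary outcomes".
- **Instruments.** Under Outcome measures, the Actiwatch "will be used to objectively assess sleep patterns", and PSQI, ISI and SF-12 record what participants report. For cognition: "To detect subtle cognitive changes, a battery of cognitive assessments will be used to evaluate various domains of cognition". That battery is ADAS-Cog, digit span, the Hong Kong List Learning Test and the Color Trails Test.
- **Analysis.** Data analysis plans a repeated-measures ANOVA that compares the arms on change over the three time-points.

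No common assessor training, inter-rater check or agreement figure for RA1 and RA2 is given. The fidelity monitoring section covers delivery of the intervention, not outcome testing.

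**The concern.** The cognitive tests depend on how an examiner gives and scores them. With RA1 at T0 and RA2 at T1 and T2, assessor and time are confounded on these tests for every T0-T1 and T0-T2 change. Two consequences follow.

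1. If RA2 scores systematically higher or lower than RA1, both arms appear to change. The time effect in the ANOVA, and any statement about change within an arm, then mixes real change with the switch of assessor.
2. If the two assistants differ by varying amounts from one participant to another, that variation enters each change score and widens its SD. Under Study participants, the pilot is meant to supply the effect size for sizing a full-scale RCT. A wider SD of change makes the standardised cognitive effect smaller.

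The stated reason for RA2 explains why the therapist should not test after treatment. It does not explain why RA2 should not also test before it. T0 precedes randomisation, so there is no allocation for RA2 to learn at that visit.

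**Working it through.** **Inputs from the documents.** 60 participants, 30 per arm, 1:1; two-sided 0.05; contrast of between-arm difference in change. The plan states no power, SD, test-retest correlation or inter-rater figure, so nothing can be reproduced beyond 2 × 30 = 60.

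**Assumptions (none in the documents).** Total SD at each visit = 1. Same-assessor correlation between T0 and follow-up = r. Assessor-by-participant share of variance = s, so the correlation across two assessors is r - s. The central case is r = 0.6 with s from 0.02 to 0.10.

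**Step 1: a constant RA2-minus-RA1 difference δ.** Mean change is (true change + δ) in each arm. The between-arm difference is free of δ; each arm's own change is not. A simulation (20,000 trials, 30 per arm, r = 0.6, assumed effect 0.5 SD) shows this:

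| δ (SD) | Between-arm difference in change | SE | Control-arm change |
|---|---|---|---|
| 0 | 0.502 | 0.230 | 0.0 |
| 0.5 | 0.502 | 0.230 | 0.5 |
| 1.0 | 0.502 | 0.230 | 1.0 |

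The closed form agrees: √[(2/30) × 2(1 - 0.6)] = √0.0533 = 0.231.

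**Step 2: assessor-by-participant variation.**

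- Variance of change: 2(1 - r) with one assessor, 2(1 - r + s) with two.
- SE ratio, change score: √[(1 - r + s)/(1 - r)].
- SE ratio, baseline-adjusted: √[(1 - (r - s)²)/(1 - r²)].

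At r = 0.6:

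| s | Change-score SE ratio | Baseline-adjusted SE ratio | Per-arm n needed to match 30 with one assessor | Power if 80% with one assessor |
|---|---|---|---|---|
| 0.02 | √(0.42/0.40) = 1.025 | √(0.6636/0.64) = 1.018 | 30 × 1.05 = 31.5, so 32 | 78.1% |
| 0.05 | √(0.45/0.40) = 1.061 | √(0.6975/0.64) = 1.044 | 30 × 1.125 = 33.75, so 34 | 75.2% |
| 0.10 | √(0.50/0.40) = 1.118 | √(0.75/0.64) = 1.083 | 30 × 1.25 = 37.5, so 38 | 70.7% |

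Power is for the change-score analysis.

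**Step 3: other values of r, with s from 0.02 to 0.10.**

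| r | Rise in SE, change score | Rise in SE, baseline-adjusted |
|---|---|---|
| 0.5 | 2.0% to 9.5% | 1.3% to 5.8% |
| 0.7 | 3.3% to 15.5% | 2.7% to 12.0% |
| 0.8 | 4.9% to 22.5% | 4.3% to 19.0% |

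**Step 4: effect passed on.** An effect standardised by the SD of change is divided by the change-score ratio. At r = 0.6 it is multiplied by 1/1.025 = 0.98 at s = 0.02 and by 1/1.118 = 0.89 at s = 0.10.

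Steps 2 to 4 describe a single T0-to-follow-up contrast. T1-T2 change stays with RA2 and is unaffected.

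**The case against.** The case for leaving the plan alone is substantial.

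- **The primary outcomes are largely out of reach.** Sleep pattern comes from a device and sleep quality from participant report. A reader might infer that all change scores cross assessors. They do not: T1-T2 change has one assessor, Actiwatch is unaffected, and the questionnaires are little affected. This stands and confines the point to the secondary cognitive battery.
- **The treatment comparison is not biased.** A reader might infer that it is. Step 1 shows that a constant difference cancels in the contrast the plan analyses. This stands.
- **The split has a stated purpose.** "To minimize biases, another research assistant (RA2) who is blinded to the group allocation" is the opening of the sentence that introduces RA2, and RA1, as therapist, could not be blind at follow-up. This stands for T1 and T2, but it gives no reason for having RA1 test at T0.
- **Within-arm change is hard to read anyway.** Participants are selected on low HK-MoCA and PSQI above 5 and then retested, so regression to the mean and practice can move raw scores whoever tests. Using RA2 throughout removes one confounder, not all of them.
- **The size is assumed.** A reader might reach larger figures by multiplying r by an inter-rater ICC. With r = 0.8 and ICC 0.80, the change-score ratio is √[(1 - 0.64)/(1 - 0.80)] = 1.34. The documents give no ICC. An ordinary ICC can also include a constant rater shift, which cancels, and random error already counted in r. The 34% figure should not be used.

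**Conclusion.** The point holds in a limited form. As the plan reads, T0-T1 and T0-T2 changes on the four cognitive tests cross assessors for every participant, and no reason is given for RA1 doing the baseline tests. The confounding of time with assessor on these tests follows from the design and needs no assumption about r or s; how far it distorts the time effect depends on the unknown RA1-RA2 difference.

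The loss of precision does depend on assumptions. It is zero if there is no assessor-by-participant variation. At r = 0.6 and s = 0.02 to 0.10 it is about 2.5% to 12% on the SE of the difference in change, or about 2% to 8% with baseline adjustment, and more at higher r.

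The documents do not support reading this as a threat to the primary sleep outcomes or as a bias between arms. Severity is minor: the outcomes are secondary, the trial is a 60-person pilot, and the size is unknown. It is still worth acting on, because the remedy is cheap and baseline cannot be collected again once treatment has begun.

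**What to change.** In Study design, state that RA2 administers the cognitive battery at T0, before randomisation, as well as at T1 and T2. RA1 keeps recruitment, consent and eligibility screening. The PSQI should stay with RA1 at T0 because it is both an entry criterion and an outcome; moving it would mean giving it twice or splitting the screening visit.

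The cost is a short change of text and about 60 baseline cognitive assessments moved from RA1 to RA2. RA2 must be available throughout recruitment at the centres of both organisations. The documents do not give RA2's hours, so this needs checking.

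If RA2 cannot cover baseline, a weaker alternative is to train both assistants together on the battery and report an inter-rater check. In that case the report should not interpret the time effect or within-arm change on the cognitive tests as change in participants.
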